8.3 Exclusion Criteria

- 1. Have a neuromuscular, orthopedic or other non-cardiac condition that prevents patient from exercise testing on a bicycle ergometer or from walking in a hallway
- 2. Non-cardiac condition limiting life expectancy to less than one year, per physician judgment
- 3. Current or anticipated future need for nitrate therapy
- 4. Valve disease (> mild aortic or mitral stenosis; > moderate aortic or mitral regurgitation)
- 5. Hypertrophic cardiomyopathy
- 6. Infiltrative or inflammatory myocardial disease (amyloid, sarcoid)
- 7. Pericardial disease
- 8. Primary pulmonary arteriopathy
- Have experienced a myocardial infarction or unstable angina, or have undergone percutaneous transluminal coronary angiography (PTCA) or coronary artery bypass grafting (CABG) within 60 days prior to consent, or requires either PTCA or CABG at the time of consent
- 10. Other clinically important causes of dyspnea such as morbid obesity or significant lung disease defined by clinical judgment or use of steroids or oxygen for lung disease
- 11. Systolic blood pressure < 110 mmHg or > 180 mm Hg
- 12. Diastolic blood pressure < 40 mmHg or > 100 mmHg
- 13. Resting heart rate (HR) > 100 bpm
- 14. A history of reduced ejection fraction (EF<50%)
- 15. Implanted metallic device which will interfere with MRI examination (in patients without atrial fibrillation)
- 16. Severe renal dysfunction (estimated GFR < 20 ml/min/1.73m² by modified MDRD equation) GFR (mL/min/1.73 m²) = 175 x (S_{cr})^{-1.154} x (Age)^{-0.203} x (0.742 if female) x (1.210 if African American) (conventional units)
- 17. Women of child bearing potential who do not have a negative pregnancy test at study entry and who are not using effective contraception
- 18. Hemoglobin <10 g/dL
- 19. Patients taking alpha antagonists or cytochrome P450 3A4 inhibitors (ketoconazole, itraconazole, erythromycin, saquinavir, cimetidine or serum protease inhibitors for HIV).
- 20. Patients with retinitis pigmentosa, previous diagnosis of nonischemic optic neuropathy, untreated proliferative retinopathy or unexplained visual disturbance
- 21. Patients with sickle cell anemia, multiple myeloma, leukemia or penile deformities placing them at risk for priapism (angulation, cavernosal fibrosis or Peyronie's disease)
- 22. Patients with severe liver disease (AST > 3x normal, alkaline phosphatase or bilirubin > 2x normal)
- 23. Consistent with ACC/AHA guidelines, persons with dyspnea and risk factors for coronary artery disease, should have had a stress test and those patients with a clinically indicated stress test demonstrating significant ischemia within a year prior to enrollment would be excluded

Up to 58 patients with chronic atrial fibrillation will be enrolled in the study Once 58 patients with chronic atrial fibrillation have been enrolled, the DCC and DSMB will review the characteristics (atrial fibrillation versus sinus rhythm) of all patients enrolled and will increase this limit if needed to insure adequate enrollment to address the primary endpoint.

9. TREATMENT INTERVENTIONS

9.1 Intervention

The therapeutic intervention is double blinded therapy with placebo or the PDE-5 inhibitor sildenafil (as Revatio[®]). Study drug therapy will be given for 24 weeks starting with 20 mg by mouth three times a day (tid) for 12 weeks. If that dose is well tolerated, the dose will be increased to 60 mg tid at week 12 for the remaining 12 weeks of the study. Patients unable to tolerate the 60 mg tid will be maintained on the 20 mg tid dose. The active and placebo study medication will appear identical to preserve the double blind design of the study. If patients develop side effects thought potentially related to study drug (including but not limited to headache, flushing, dizziness, orthostatic lightheadedness, dyspepsia, nasal congestion, diarrhea, rash, visual disturbance), the dose will be adjusted to the previously tolerated dose. As recommended for patients with HF, patients will be encouraged to weigh daily and record weights. If patients have experienced enhanced responsiveness to their diuretic dosage (decreased weight *and* symptoms of over-diuresis such as lightheadedness), consideration can be given to reducing the diuretic dose rather than the study drug.

9.2 Control Group

The control group in this study will include patients randomized to placebo medication. Study drug (sildenafil or placebo) will be given in a double blind fashion and all patients will undergo identical study procedures including dose titration.

9.3 Concomitant Therapies

Current guidelines for management of DHF stress control of hypertension, rate control for patients with atrial fibrillation, avoidance of tachycardia in patients in normal sinus rhythm, maintenance of sinus rhythm, use of diuretics and revascularization if diastolic dysfunction is thought related to ischemia⁴⁴. These recommendations are based on consensus opinion as there have been few clinical trials in DHF and no therapy has been proven to improve clinical outcomes (see section 4.3). Thus, treatment with agents to control blood pressure and maintain volume status is expected but no specific concomitant therapies are specified.

Study exclusion criteria outline drugs which can not be used due to concern over drug interaction (see exclusion criteria, section 8.3). These include nitrate preparations as well as alpha antagonists or cytochrome P450 3A4 inhibitors or serum protease inhibitors for HIV. If the patient develops clear indication for nitrates (angina which can not be managed with alternative antianginals), the patient will need to be withdrawn from the study. If the need for nitrates is emergent or urgent, the treatment assignment in the patient should be obtained emergently from the DCC so that patients treated with placebo could start treatment with nitrates immediately. If the patient was on active therapy, the exact time after the last dose of sildenafil when nitrates can be safely administered is not well defined. Although plasma levels of sildenafil at 24 hours post dose are much lower than at peak concentration, it is unknown whether nitrates can be safely co-administered at this time point. Thus, it is recommended that nitrates should not be administered to any patient previously on active study drug prior to 5 days after the last dose of sildenafil. Should there be an urgent need for nitrate administration, they should be administered in a monitored inpatient setting.

In patients with a history of volume retention or hypertension, standard therapy will specify a low sodium diet but no specific instructions regarding diet will be provided as part of the study. Daily aerobic exercise is recommended for patients with HF as tolerated but no specific recommendations for activity will be provided as part of this study.

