12.3 Blinding of Study Personnel

All enrolled patients will be assigned a study number and study drug (placebo or sildenafil) will have an identical appearance and will be allocated according to a predetermined randomization scheme. The DCC will allocate study drug and the study staff will not have access to information regarding whether the patient is on active or placebo therapy. As sildenafil may commonly have characteristic benign (enhanced erectile function) or rarely adverse (priapism) side effects in male patients, study subjects will be encouraged at consent and enrollment not to discuss any non-adverse changes in sexual function with the study staff. However, all patients will be assessed for adverse events at the serial study visits as outlined above. If a patient has experienced an adverse effect likely or potentially attributable to the study drug, the decision to discontinue the drug will be made without unblinding the patient or the study staff unless deemed urgent to care of the patient. In this case, the DCC will supply the information and the patient will be removed from the study.

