12.4 Unblinding Procedures

The DCC Medical Monitor will be available to the attending physician to help consider the need for unblinding on a case by case basis. Unblinding will be permitted ONLY for the reason of subject safety. Specifically, the blind should be broken only for serious, unexpected and drug-related AEs or when required by local regulatory authorities, when the knowledge of treatment assignment is needed for subject safety. The site investigator must notify the DCC prior to the unblinding of any subject. The site investigator should direct the attending physician to contact the DCC Medical Monitor who will verify that a patient safety issue requires unblinding and will carry out the unblinding procedure. In an emergency, if the site investigator is not immediately available, the attending physician should contact the DCC Medical Monitor directly. Every effort should be made to maintain the blind for the site investigator and study coordinator. In the event of a blind breaking, only the treatment assignment for the subject in question will be revealed.

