13.3 Evaluations for Drop-Outs and Withdrawals

If a subject drops out of the study for any reason, the subject will be encouraged to complete as many of the study procedures as they will agree to as outlined in section 13.1 above.

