18.2 Analysis Policies

A statistical analysis plan will be completed before the data are analyzed in an unblinded fashion. Due to clinical interest in departures from both sides of the null hypothesis, all test statistics will be twosided. The trial results will be reported according to guidelines specified in the CONSORT statement^{121,122}. A flow diagram describing screening, recruitment, randomization, dropout, and vital status will be included in the primary manuscript. Adverse events and efficacy data will be presented by the two treatment groups. Adherence, dropout, and lost-to-follow-up will be carefully examined across the two treatment groups. Analyses of safety will be based on data from all randomized patients who received at least 1 dose of study drug. All primary analyses will be based on intent-to-treat (ITT) principles using all randomized participants.

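### Sections 9.3 and 12.3 take patients out of the study, not only off study drug, and this is not reconciled with the follow-up, unblinding and intention-to-treat provisions

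*Protocol*

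**What the plan says.** Two rules end participation after randomization.

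- **Section 9.3 (nitrates).** If angina cannot be managed with other antianginals, "the patient will need to be withdrawn from the study". Where the need is urgent, "the treatment assignment in the patient should be obtained emergently from the DCC".
- **Section 12.3 (adverse effects).** The decision to stop the drug is normally made blind. The exception is when unblinding is urgent for the patient's care: "In this case, the DCC will supply the information and the patient will be removed from the study".

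Four other provisions bear on the same patients.

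- **Section 12.4 (unblinding procedures).** It states no removal: "In the event of a blind breaking, only the treatment assignment for the subject in question will be revealed".
- **Section 13.3 (patients who leave early).** The rule here is one of encouragement: "If a subject drops out of the study for any reason, the subject will be encouraged to complete as many of the study procedures", to the extent that they agree.
- **Section 18.2 (analysis policies).** "All primary analyses will be based on intent-to-treat (ITT) principles using all randomized participants".
- **Section 14.2.1 (composite score).** Every participant is ranked: first by death, then by cardiovascular or renal hospitalization, then by change in MLWHFQ.

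**The concern.** Stopping a drug and leaving a trial are different events. Under intention-to-treat, a patient who stops treatment should still be measured. The protocol makes this distinction elsewhere: section 9.5 stops study drug for acute coronary syndromes, section 9.6.3 has patients discontinue study drug for hearing change, and section 12.3 itself mentions discontinuing the drug before it speaks of removal from the study. So the wording in 9.3 and 12.3 cannot safely be read as shorthand for stopping the drug.

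The triggers are also unlikely to be random. Section 9.5 lists angina and myocardial ischemia among the important side effects of sildenafil, and the trigger in 12.3 is an adverse effect that may be due to study drug. Removal could therefore be related both to outcome and to arm.

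If a site applies the wording literally, it may stop collecting week-24 peak VO2, MLWHFQ, and later deaths and hospitalizations. The primary model in section 18.5 uses the week-24 change. An analysis plan can choose how to handle missing values, but it cannot recover data that were never collected.

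**Working it through.** **1. The passages side by side**

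| Situation | Section | Effect on study drug | Effect on study participation |
|---|---|---|---|
| Acute coronary syndrome | 9.5 | stopped | none stated |
| Tinnitus or hearing loss | 9.6.3 | discontinued | none stated |
| Clear nitrate indication | 9.3 | not stated separately | withdrawn |
| Urgent unblinding after an adverse effect | 12.3 | not stated separately | removed |
| Unblinding in general | 12.4 | none stated | none stated |
| Drop-out for any reason | 13.3 | none stated | remaining procedures encouraged |

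An acute coronary syndrome thus stops the drug, while angina needing nitrates ends participation. Urgent unblinding ends participation under 12.3 but not on the face of 12.4. A site cannot tell from the text whether outcome collection continues.

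**2. The plan's own sample size**

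Inputs from section 18.1.1: two-sample t-test, two-sided alpha 0.05, treatment effect 1.2 ml/kg/min, SD 2.5 ml/kg/min, up to 25% missing data, about 215 patients. Allocation is 1:1 (section 6).

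- Evaluable patients for 85% power by the noncentral t: 158, which matches the table.
- Inflated for 25% missing: 158 / 0.75 = 211, close to the stated 215.
- Conversely, 215 × 0.75 = 161 evaluable, which gives 85.7% power.

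The sample size therefore reproduces. If removals under the two rules fall within the 25% allowance, the stated power is unaffected. If 5% or 10% were lost on top of it, about 150 or 140 would be evaluable, with power of about 83% or 81%. The issue is bias more than power.

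**3. How large the bias could be**

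Let *w* be the share of an arm that is removed, and *g* the mean 24-week change in removed patients minus that in retained patients. The retained patients' mean then differs from the full-arm mean by −*w* × *g*. If *g* is the same in both arms:

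shift in treatment difference = −(*w* active − *w* placebo) × *g*

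Neither *w* nor *g* is in the documents. All values below are assumptions.

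| Removed, active | Removed, placebo | *g* (ml/kg/min) | Shift (ml/kg/min) | Share of 1.2 |
|---|---|---|---|---|
| 5% | 5% | −2.5 | 0 | 0% |
| 3% | 0% | −2.0 | +0.06 | 5% |
| 5% | 2% | −2.5 | +0.075 | 6% |
| 2% | 5% | −2.5 | −0.075 | −6% |
| 8% | 0% | −2.0 | +0.16 | 13% |
| 10% | 0% | −2.5 | +0.25 | 21% |

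For scale, the standard error of the difference with 161 evaluable patients is 2.5 × √(4/161) = 0.39 ml/kg/min. The sign depends on which arm loses more patients, and the shift is zero when removal and gaps are equal.

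**The case against.** The strongest reply is that section 13.3 already deals with this. Its heading covers withdrawals as well as drop-outs, it applies whatever the reason, and it is the only section that says what happens afterwards. On that reading the week-24 tests are still sought, and nothing is necessarily lost. This stands in part: a reader might infer that these patients' outcomes are certainly missing, and no passage says so. But the operative sentence concerns a subject who drops out, only encourages procedures, and does not mention continued ascertainment of vital status or hospitalizations after protocol-mandated removal.

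A reader might also infer that any breaking of the blind ends participation. The text does not support that. Removal is stated in 12.3 only for urgent unblinding after an adverse effect, and in 9.3 through the nitrate rule. The nitrate trigger is narrow too, since section 8.3 excludes current or anticipated nitrate need, recent infarction or unstable angina, and significant ischemia on a clinically indicated stress test.

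Nor is intention-to-treat abandoned. No passage excludes these patients from analysis, section 18.2 commits to examining dropout by arm, and section 18.1.1 allows for missing data. Section 18.6 specifies a worst-rank approach for the composite, and a mixed model with inverse-probability-weighted sensitivity analyses for peak VO2 and walk distance. Handling of missing primary data may be in the analysis plan, which is not shown. All of this limits the harm, but none of it replaces collecting the data.

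Two further points stand. If the trigger is itself a cardiovascular admission, the patient is already placed in the middle tier of the composite, and only a later death would change the tier. And some week-24 exercise tests may not be obtainable in patients with refractory angina, whatever the wording.

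**Conclusion.** The finding is an inconsistency in the protocol that carries a risk of informative missing data. It is not a demonstrated failure of intention-to-treat, nor an error in the sample size. Sections 9.3 and 12.3, read literally, end participation after events that may relate to treatment and outcome, while sections 12.4, 13.3, 14.2.1 and 18.2 presuppose or allow continued observation.

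The size and direction of any bias cannot be derived from the documents. The non-zero shifts of 0.06 to 0.25 ml/kg/min, in absolute size, assume unequal removal between arms and an outcome gap of 2.0 to 2.5 ml/kg/min. The larger ones assume removal from one arm only. They illustrate the mechanism and should not be quoted as an estimate. The change is nevertheless worth making, because it is cheap and because the loss, if it occurs, cannot be repaired at the analysis stage.

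**What to change.** Reconcile the passages. State in sections 9.3 and 12.3 that a patient who meets either rule remains in the trial for outcome collection to week 24, with the patient's consent. That covers vital status, hospitalizations, MLWHFQ, and the exercise tests of section 13.1 where the investigator judges them permissible. Cross-refer both sections to 13.3, make 13.3 say that it applies to these patients, and align 12.3 with 12.4 on whether unblinding affects participation. State that the data so collected enter the intention-to-treat analyses under section 18.2.

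The clinical rules on when nitrates, stopping of study drug or unblinding are needed are not touched. Because 9.3 deals with study drug only through the withdrawal sentence, the revised wording must preserve whatever the sponsor intends there about the drug.

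The cost is a few sentences of protocol text and continued contact with a small number of patients on visits already scheduled.

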9.4 Dose Justification (also see Appendix 3; Section 22.3)

Most studies suggesting benefit of sildenafil in humans with SHF have utilized a single dose to assess acute effects. The early studies of chronic therapy in humans with PH were small and ill suited to assess dose response. Thus, the justification for the dosing chosen in the RELAX study is based on the recently published larger trial in pulmonary arteriopathies unrelated to HF which explored dose responsiveness ⁶⁸ and the seminal animal (mouse) study ⁵¹.

In the Sildenafil Use in Pulmonary Arterial Hypertension (SUPER) study ⁶⁸, oral doses of 20, 40 and 80 mg tid were compared to placebo in patients with symptomatic (NYHA class II-III, mean age 57 years) PH. No dose response was evident for the primary endpoint (6 minute walk distance) *or for tolerability*. However, the data presented suggest the presence of a dose response with decreases in heart rate, pulmonary artery pressure, and pulmonary vascular resistance appearing most dramatic with the highest dose.

In the seminal mouse study showing anti-hypertrophic and anti-fibrotic effects and effects to preserve LV systolic and diastolic function, the sildenafil dose was 100 mg/kg/day⁵¹. This dose was postulated to be equivalent to approximately 1 mg/kg/day in man due to a "near 100-fold higher rate of metabolism of sildenafil in the mouse". In a study of pharmacokinetics of sildenafil in mouse and man, oral bioavailability in mice (17%) is approximately 50% that observed in humans (38%), the volume of distribution is similar (1.0 l/kg in mouse versus 1.2 l/kg in man) but metabolism is faster with an elimination half life of 1.3 hours vs 3.7 hours in mouse vs man⁸³. The maximal concentration at equivalent oral dose (1 mg/kg) was 30 ng/ml in mouse and 212 ng/ml in humans. The time to peak concentration was 0.5 hours in mouse and 1.2 hours in man. Thus, these data suggest that clearance is faster and that to achieve a similar peak or steady state concentration, the equivalent dose in humans would be significantly less than used in the mouse, although not clearly 100% less. Assuming an average body size of 70-90 kg, the planned dose range is 0.66- 2.57 mg/kg/day. Thus, the planned dose range is proportion-al to that used in the mouse where dramatic effects on myocardial structure and function were observed.

It is acknowledged that the absence of a relationship between the dose of sildenafil and the change in 6 minute walk distance in the SUPER trial may suggest that up-titration to a dose beyond 20 mg tid in RELAX is unnecessary. Recent studies suggest that binding of cGMP and PKG mediated phosphorylation of PDE-5 enhance binding (of cGMP). Binding of sildenafil produces similar conformational changes as seen with binding of cGMP (promoting further sildenafil binding) and further enhances binding by increasing intracellular cGMP and thus PKG mediated phosphorylation of PDE-5. This further increases sildenafil binding. Based on these observations regarding the biology of PDE-5 and sildenafil, one could hypothesize that the duration of sildenafil binding to PDE-5 is longer than would be predicted from it's pharmacokinetics and that dose (or plasma levels) do not correlate linearly with enzyme binding and biological effect⁸⁴. These remain intriguing and important but as yet unproven hypotheses. However, there are only limited data regarding the dose response of pulmonary or peripheral vascular, myocardial, renal, neurohumoral or clinical outcome effects of sildenafil in pulmonary hypertension or systolic HF (reviewed in detail in Appendix 3). Some of these data support the importance of a dose up-titration strategy while other data do not. Unfortunately, there are no data concerning the dose response in the unique syndrome of DHF where the pathophysiology and dose responsiveness may differ from erectile dysfunction, pulmonary hypertension and systolic heart failure. Thus, acknowledging the size and the phase II nature of this trial in DHF, a dose which will maximize efficacy is chosen and some exploratory dose response data will be obtained. Specifically, in an exploratory analysis we will compare exercise capacity in sildenafil treated patients after 12 weeks at 20 tid to that observed after 12 weeks on 60 tid. Further, all studies will be performed at near peak sildenafil levels (45-120 minutes after last dose) and levels will be checked at the time of the exercise study at 12 and 24 weeks. These data will provide further information regarding the relationship between dose and plasma levels and therapeutic response.

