6. Change in peripheral vascular function (effective arterial elastance (Ea), systemic vascular resistance (SVR) and aortic thickness and distensibility) at 24 weeks

7. Change in pulmonary hemodynamics (Doppler estimated pulmonary artery systolic pressure (PASP)) at 24 weeks

8. Change in neuroendocrine function (Cyclic guanosine monophosphate (cGMP), N-terminal pro-brain natriuretic peptide (NT-proBNP) and aldosterone) at 24 weeks

9. Change in renal function (creatinine, estimated glomerular filtration rate (GFR), cystatin C and diuretic dose) at 24 weeks

Pre-specified subgroup analysis will include comparison of the effect of therapy in patients with:

- 1. LV mass index above and below the median at entry into the study.
- 2. Estimated PASP above and below the median at entry into the study
- 3. Dose of sildenafil achieved
- 4. Presence of atrial fibrillation
- 5. Differences in background therapy

Primary Hypothesis: As compared to placebo, chronic PDE-5 inhibition will result in greater improvement in exercise performance as measured by peak VO_2 in DHF after 24 weeks of double blinded therapy.

Secondary Hypotheses:

- 1. As compared to placebo, chronic PDE-5 inhibition will result in greater improvement in clinical status at 24 weeks.
- 2. As compared to placebo, chronic PDE-5 inhibition will result in greater improvement in submaximal exercise capacity as assessed by 6 minute walk distance at 12 and 24 weeks.
- 3. As compared to placebo, chronic PDE-5 inhibition will result in improved exercise performance as measured by peak VO₂ after 12 weeks.
- 4. As compared to placebo, chronic PDE-5 inhibition will result in greater improvement in other measures of exercise capacity (exercise time and VAT) at 12 and 24 weeks.
- 5. As compared to placebo, chronic PDE-5 inhibition will result in greater improvement in quality of life as assessed by the MLWHFQ score at 12 weeks and 24 weeks.
- 6. As compared to placebo, chronic PDE-5 inhibition will result in greater reduction in LV mass, serological markers of LV fibrosis, diastolic dysfunction, peripheral vascular dysfunction, pulmonary vascular dysfunction, humoral activation and renal dysfunction at 24 weeks.
- 7. Increasing the dose of sildenafil from 20 mg tid to 60 mg tid will result in further improvement in exercise performance as measured by peak VO_2 and 6 minute walk distance.

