3. SPECIFIC AIMS AND OBJECTIVES / HYPOTHESES

This is a double-blind, placebo controlled study testing the hypothesis that chronic PDE-5 inhibition (sildenafil 20 mg tid for 12 weeks followed by 60 mg tid for 12 weeks) improves exercise capacity (primary endpoint) and clinical status (secondary endpoint) in patients with DHF. The study also measures the effect of this therapy on key pathophysiological parameters which are postulated to impact clinical status and exercise performance in DHF. Approximately 215 patients will be enrolled over a planned 3.25 year enrollment period.

Primary Hypothesis: As compared to placebo, chronic PDE-5 inhibition will result in improved exercise performance as measured by peak VO_2 in DHF after 24 weeks of double blinded therapy.

Secondary Hypotheses:

- 1. As compared to placebo, chronic PDE-5 inhibition will result in greater improvement in global clinical status at 24 weeks.
- 2. As compared to placebo, chronic PDE-5 inhibition will result in greater improvement in submaximal exercise capacity as assessed by 6 minute walk distance at 12 and 24 weeks.
- 3. As compared to placebo, chronic PDE-5 inhibition will result in improved exercise performance as measured by peak VO₂ in DHF after 12 weeks.
- 4. As compared to placebo, chronic PDE-5 inhibition will result in greater improvement in other measures of exercise capacity (exercise time and VAT) at 12 and 24 weeks.
- 5. As compared to placebo, chronic PDE-5 inhibition will result in greater improvement in quality of life as assessed by the MLWHFQ score at 12 weeks and 24 weeks.
- 6. As compared to placebo, chronic PDE-5 inhibition will result in greater reduction in LV mass, serological markers of LV fibrosis, diastolic dysfunction, peripheral vascular dysfunction, pulmonary vascular dysfunction, humoral activation and renal dysfunction at 24 weeks.
- 7. Increasing the dose of sildenafil from 20 mg tid to 60 mg tid will result in improvement in exercise performance as measured by peak VO₂ and 6 minute walk distance.

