15. METHODS TO PROMOTE ADHERENCE TO THE INTERVENTIONS

Adherence to study drug: Patients will be instructed to bring all used and remaining bottles of study drug to each study visit. The percent compliance will be calculated at each study visit. Adherence to study procedures: Adherence to study procedures will be enhanced by the following factors:

- 1. At recruitment and consent visits, the entire study will be carefully explained to the patient and figures used to indicate what procedures and visits will be required of the patient. The potential participant will be asked to carefully consider their ability to participate in the study and specifically their willingness to perform a total of four cardiopulmonary exercise tests.
- 2. When feasible, use of a clinically indicated screening CPXT will familiarize the patient with the procedure and better enable the patient to determine whether they are able to perform subsequent baseline, 12 and 24 week CPXT. Further, patients with non-cardiac dyspnea due to frailty, motivational factors, deconditioning and pulmonary disease will be identified and excluded (patients must meet RER≥1.0) since these patients are less likely to perform subsequent CPXT.
- 3. Designation of VO₂ as the primary endpoint emphasizes its importance to both the investigator and the patient and will enhance compliance.
- 4. Adherence to study drug and procedures will be promoted via the study visits and monthly phone visits when not seen in person.
- 5. There is currently no therapy proven to affect outcomes in DHF. This factor generally enhances compliance with an RCT of novel therapies.
- 6. Performance of RELAX within the limited number of sites in the HFN under the direct supervision of the principal investigators involved in the HFN steering committee should enhance compliance with the baseline and follow up studies.
- 7. Data completeness at each site will be carefully monitored by the DCC and those sites not providing complete follow up data will be contacted and strategies to enhance compliance identified.
- 8. In general, event rates in RCT are lower than those observed in observational studies of HF and this was observed in DHF even in a large RCT restricted to elderly persons (PEP-CHF)⁴⁷. Power calculations indicate adequate power even considering death rates at 6 months similar to those observed in community based observational studies.

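### Secondary hypothesis 7 (raising the dose improves exercise capacity) is served only by an exploratory within-arm comparison, which cannot separate the dose increase from change over time that placebo patients would also show

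*Protocol*

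**What the plan says.** The Executive Summary lists as secondary hypothesis 7: "Increasing the dose of sildenafil from 20 mg tid to 60 mg tid will result in further improvement in exercise performance", measured by peak VO2 and 6-minute walk distance. Section 3 repeats it in nearly the same form: "Increasing the dose of sildenafil from 20 mg tid to 60 mg tid will result in improvement in exercise performance". Hypotheses 1 to 6 each name placebo as the comparator; hypothesis 7 names none.

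Section 9.4 describes the comparison of the two dose periods, and calls it exploratory: "we will compare exercise capacity in sildenafil treated patients after 12 weeks at 20 tid to that observed after 12 weeks on 60 tid". Both sides of the comparison are sildenafil patients.

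Section 9.1 fixes the order, "starting with 20 mg by mouth three times a day (tid) for 12 weeks", with escalation at week 12 if the dose is tolerated. It adds: "Patients unable to tolerate the 60 mg tid will be maintained on the 20 mg tid dose". Section 9.2 says of the two arms that "all patients will undergo identical study procedures including dose titration", and section 13.1 schedules the exercise test and the 6-minute walk at weeks 12 and 24 without distinguishing the arms.

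Section 18.6 specifies a mixed model for repeated measures (MMRM) comparing the slopes of peak VO2 and 6-minute walk distance between arms. It neither mentions hypothesis 7 nor names the week-12-to-24 change as a contrast. Section 18.7 lists dose achieved as a subgroup. That concerns who reached which dose after randomization and is not tied to hypothesis 7 either.

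**The concern.** No sildenafil patient has 60 mg tid first, and no arm is kept on 20 mg tid by design, so within the sildenafil arm dose and time on study coincide. A change between weeks 12 and 24 may reflect the higher dose. It may also reflect a further 12 weeks of exposure, or things that happen on placebo too. The protocol itself describes several of these:

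- Repeat testing: section 15 asks patients to consider "their willingness to perform a total of four cardiopulmonary exercise tests".
- Progression: section 18.1.2 cites a cohort in which, over 6 months, 13% died, 27% declined in functional status and 10% improved.
- Background therapy: section 9.3 fixes no concomitant regimen, and sections 9.1 and 9.5.1 allow the diuretic dose to be reduced.

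Upward drift would be credited to the higher dose; downward drift would hide a benefit or look like harm. At stake is what the trial reports about escalation, a question section 9.4 calls open in this disease. The placebo arm already provides the data needed to remove drift common to both arms.

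**Working it through.** **1. The plan's own figures.** Section 18.1.1 uses a two-sample t-test, two-sided alpha 0.05, an effect of 1.2 ml/kg/min, an SD of 2.5 and 85% power. An exact noncentral-t calculation gives 158 analysable patients, as tabulated, and all 16 legible cells of the table reproduce. Allowing for 25% missing data, 158 / 0.75 = 211, in line with the stated figure of about 215. The sample size is not in dispute. It implies 158 / 2 = 79 evaluable patients per arm.

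**2. The within-arm comparison when dose has no effect.** The protocol states no test for it. As an illustration, take a two-sided 5% paired t-test of week 24 minus week 12 in n = 79 sildenafil patients, with a true dose effect of zero and a drift d common to both arms. The noncentrality is d / (SD / √n). For d = 0.3 and SD 2.5 this is 0.3 / (2.5 / √79) = 0.3 / 0.281 = 1.07, and the rejection rate from the noncentral t with 78 df is 18.4%. The other values follow in the same way:

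| Assumed drift (ml/kg/min) | SD 2.5 | SD 2.0 | SD 1.3 |
|---|---|---|---|
| 0 | 5% | 5% | 5% |
| 0.2 | 10.8% | 14.2% | 27.2% |
| 0.3 | 18.4% | 26.1% | 52.6% |
| 0.5 | 41.9% | 59.3% | 92.2% |

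With n = 80 the figures are essentially the same (SD 2.5: 19% and 42%; SD 2.0: 26% and 60%, for drifts of 0.3 and 0.5). The SDs of 2.5 and 2.0 are values in the section 18.1.1 table, and 1.3 is the limited DHF figure given there. Using any of them for the 12-to-24-week change is an assumption, and so is every drift value.

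**3. The placebo-adjusted contrast.** Let D be the mean week-24-minus-week-12 change in an arm. In D(sildenafil) − D(placebo), a drift common to both arms cancels, so the rejection rate stays at 5% for any d. With 79 per arm and equal SDs, the standard error is SD × √(2/79) instead of SD × √(1/79), a ratio of √2 ≈ 1.4. The detectable difference at 85% power, (1.960 + 1.036) × SE, is:

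| SD | Within-arm | Placebo-adjusted |
|---|---|---|
| 2.5 | 0.84 | 1.19 |
| 2.0 | 0.67 | 0.95 |
| 1.3 | 0.44 | 0.62 |

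The smaller within-arm figures are valid only if drift is zero.

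**4. Whether the section 18.6 slope already answers the question.** With complete data at weeks 0, 12 and 24 and compound symmetry, the fitted linear slope is (−12·y0 + 0·y12 + 12·y24) / 288 = (y24 − y0) / 24. Week 12 has no weight, so the slope difference does not isolate what happens after escalation.

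**The case against.** Section 9.4 calls the comparison exploratory and gives the trial's size and phase II nature as the reason. It states no test, alpha or decision rule, and it does not cite hypothesis 7. Section 18.2.1 assigns the 0.05 level only to the primary endpoint. A reader might infer that hypothesis 7 will be formally declared true or false at an inflated error rate. The document does not support that: the percentages above describe a test the protocol does not state.

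A reader might also infer that the plan ignores placebo altogether. It does not. Peak VO2 and 6-minute walk distance are compared with placebo at both week 12 and week 24, and the MMRM includes both arms, so shared drift should be visible to anyone who looks. Nor does the protocol show that drift of 0.3 or 0.5 ml/kg/min occurs. It could be zero or negative, and learning between weeks 12 and 24 may be small in patients already tested and required to reach an RER of at least 1.0.

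Dropout might be counted among the quantified biases. It is not: the calculation uses patients tested at both visits, and the placebo contrast would not remove differential dropout.

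These points limit the size and status of the concern. They do not rescue the comparison: section 9.4 names the comparator, and it is the same arm at an earlier time. Choosing the contrast could be left to the statistical analysis plan, which is not at hand, but here the protocol has already described a weaker one.

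**Conclusion.** The point holds as a correctable weakness in an exploratory analysis. A hypothesis listed as secondary has, as its only described comparison of the two dose periods, a before-after contrast in one arm under a fixed dose order. That contrast cannot separate the dose increase from time effects shared with placebo.

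The illustrative false-positive rates (5% with no drift, about 18 to 26% at 0.3 ml/kg/min, about 42 to 60% at 0.5) rest on an assumed drift, an assumed SD of 2.0 to 2.5 for the 12-to-24-week change, about 80 patients and an assumed paired test. They show sensitivity to drift and do not predict it.

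It is also unsettled whether patients held at 20 mg tid count in the week-24 side of the comparison. If they do not, that side is a tolerance-selected set.

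The primary 24-week analysis and the other comparisons with placebo are untouched. Severity is minor to moderate.

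**What to change.** In sections 9.4 and 18.6, name the analysis of hypothesis 7 as the sildenafil-minus-placebo difference in the week-12-to-24 change in peak VO2 and in 6-minute walk distance. Estimate it as a contrast from the MMRM with visit as a categorical factor, by randomized arm and in all randomized patients whatever dose they reached. Keep the within-arm change as description only.

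State two limits: the contrast estimates the dose increase together with longer exposure, and it does not remove differential dropout. Reconcile the secondary label in the Executive Summary and section 3 with the exploratory label in section 9.4.

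The cost is one sentence in 9.4, one contrast in 18.6 and no new data. The downside is the standard error, about 1.4 times that of the one-arm comparison. At SD 2.5 with 79 per arm, the detectable difference at 85% power rises from 0.84 to 1.19 ml/kg/min.
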